**After Study Discontinuation:**

Upon discontinuation of study drug, subjects will be followed every 24 weeks for survival, information on other CLL treatments, response to next therapy and progression following next therapy, and second primary malignancies (reported as SAEs). Subjects will be followed until all subjects in the study have been followed for at least 5 years from the last randomization, October 2020 (or have died/become lost to follow-up before 5 years).

FCBP with regular menstrual cycles discontinued from treatment must have a pregnancy test on day 28 after the treatment discontinuation visit. FCBP with irregular cycles discontinued from treatment must have a pregnancy test on days 14 and 28 after the treatment discontinuation visit.

SAEs will continue to be collected for the first 30 days after the treatment discontinuation visit. Following 30 days post the treatment discontinuation visit, only SAEs related to maintenance therapy will be collected for the study duration. Second primary malignancies must be reported as SAEs. This includes any second primary malignancy, regardless of causal relationship to study medication, occurring at any time for the duration of the study, from the time of signing the informed consent up to and including progression free follow-up and survival follow-up.

[REDACTED]

[REDACTED]

[REDACTED]

[REDACTED]

[REDACTED]

[REDACTED]

[REDACTED]

[REDACTED]

[REDACTED]

[REDACTED]

[REDACTED]

[REDACTED]

[REDACTED]

[REDACTED]

[REDACTED]

[REDACTED]

[REDACTED]

[REDACTED]

[REDACTED]

[REDACTED]

[REDACTED]

[REDACTED]

[REDACTED]

[REDACTED]

[REDACTED]

[REDACTED]

[REDACTED]

[REDACTED]

[REDACTED]

[REDACTED]

[REDACTED]

[REDACTED]

[REDACTED]

[REDACTED]

[REDACTED]

[REDACTED]

[REDACTED]

[REDACTED]

[REDACTED]

[REDACTED]

[REDACTED]

[REDACTED]

[REDACTED]

[REDACTED]

[REDACTED]

[REDACTED]

[REDACTED]

[REDACTED]

[REDACTED]

[REDACTED]

[REDACTED]

[REDACTED]

[REDACTED]

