### **10.3. Blinding**

This is now an open-label protocol. Therefore the dose of study drug will be identified on the package labeling (Amendment #10).

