### 16.7. Safety Evaluation

All subjects who receive at least one dose of study medication will be included in the safety analyses.

Adverse events (AE) will be classified using the Medical Dictionary for Regulatory Activities (MedDRA) classification system. The severity of the toxicities will be graded according to the NCI CTCAE version 3.0 whenever possible.

The adverse event of infection will also be analyzed according to the grading system as recommended by the IWCLL guidelines for the diagnosis and treatment of CLL [REDACTED] ([Appendix 22.4](#)).

AE frequency will be tabulated by body system, MedDRA preferred term for each treatment regimen during the Treatment Phase. In the by-subject analysis, a subject having the same event more than once will be counted only once. AEs will be summarized by worst NCI CTCAE version 3.0 grade. AEs leading to death or to discontinuation from treatment, events classified as NCI CTCAE version 3.0 Grade 3 or higher, study-drug-related events, serious adverse events (SAEs), and events of interest (including second primary malignancies) will be summarized separately.

Laboratory data will be graded according to NCI CTCAE version 3.0 severity grade. Cross tabulations will be provided to summarize frequencies of abnormalities.

For vital sign and body weight data, means, medians, standard deviations, minimum, and maximum values will be provided.

Graphical displays will be provided where useful to assist in the interpretation of results.

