## 22. APPENDICES

### 22.1. Adverse Event

An adverse event (AE) is any noxious, unintended, or untoward medical occurrence occurring at any dose that may appear or worsen in a subject during the course of a study. It may be a new intercurrent illness, a worsening concomitant illness, an injury, or any concomitant impairment of the subject's health, including laboratory test values (as specified by the criteria below), regardless of etiology. Any medical condition that was present prior to study treatment and that remains unchanged or improved should not be recorded as an AE. If there is a worsening of that medical condition, this should be considered an AE. A diagnosis or syndrome should be recorded on the AE page of the electronic Case Report Form rather than the individual signs or symptoms of the diagnosis or syndrome.

All AEs will be recorded by the Investigator(s) from the time of signing of informed consent form to 30 days after the treatment discontinuation visit. All AEs that lead to study discontinuation should be followed until resolution or stabilization. AEs will be recorded on the AE page of the CRF and in the subject's source documents.

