### **Immediate reporting of serious adverse events**

Any AE that meets the criterion for a SAE requires the completion of a SAE Report Form in addition to being recorded on the AE pages of the CRF. The Investigator(s) is required to ensure that the data on these forms is accurate and consistent. This applies to all SAEs, regardless of relationship to study drug, that occur during the study, those made known to the Investigator(s) within 30 days after a subject's treatment discontinuation visit, and those made known to the investigator(s) at anytime that are suspected of being related to study drug.

Second primary malignancies will be monitored as events of interest and must be reported as serious adverse events. This includes any second primary malignancy, regardless of causal relationship to study medication, occurring at any time for the duration of the study, from the time of signing the ICF up to and including any follow-up, observation and/or survival follow-up period. In this study, subjects will be followed until all subjects in the study have been followed for at least 5 years from the last randomization, October 2020 (or have died/become lost to follow-up before 5 years). Events of second primary malignancy are to be reported using the SAE report form and must be considered an "Important Medical Event" even if no other serious criteria apply; these events must also be documented in the appropriate page(s) of the CRF and subject's source documents. Documentation of the diagnosis of the second primary malignancy must be provided at the time of reporting as a serious adverse event (eg, any confirmatory histology or cytology results).

Grade 4 hematologic abnormalities are expected in patients with CLL, and are also observed in patients receiving lenalidomide. The investigator will use their judgement to classify the seriousness of laboratory abnormality events. Laboratory values will be captured within the study database and will be reviewed on an ongoing basis by the sponsor and (provided that it is determined that any observed individual abnormalities or patterns of abnormalities do not warrant prompt communication to Health Authorities) will be reported to Health Authorities in periodic safety reports.

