12.1. Adverse Events

Adverse events (AE) will be classified using the Medical Dictionary for Regulatory Activities (MedDRA) classification system. The severity of the toxicities will be graded according to the NCI CTCAE version 3.0 whenever possible.

The adverse event of infection will also be analyzed according to the grading system as recommended by the IWCLL guidelines for the diagnosis and treatment of CLL [REDACTED] (Appendix 22.4).

Treatment emergent adverse events (AEs) will be summarized by treatment group and overall. A treatment emergent adverse event is defined as any AE occurring or worsening on or after the first treatment of any study drug, and within 30 days after the last dose of the last study drug received. Adverse events will be summarized by treatment arm and overall. Adverse events are documented on the CRF together with their severity, according to the NCI CTCAE version 3.0 or higher, also referred to as NCI toxicity grading. For the categorization of the adverse events, the Medical Dictionary for Regulatory Activities (MedDRA[®]) dictionary (version 16.0) will be used.

AE frequency will be tabulated by body system, MedDRA preferred term for each treatment regimen during the Treatment Phase as well as for the Follow-up Phase when appropriate. In the by-subject analysis, a subject having the same event more than once will be counted only once. AEs will be summarized by worst NCI CTCAE version 3.0 grade. In the case that the AEs or event frequencies are judged to be clinically important, an exact test may be used to analyze the difference between the treatment groups. In addition, AEs of special interest (Event of Interest),

including second primary malignancies (SPM), will be defined and summarized by treatment arm.

AEs leading to death or to discontinuation from treatment, events classified as NCI CTCAE version 3.0 Grade 3 or higher, study-drug-related events, serious adverse events (SAEs) and events of interest (including second primary malignancies) will be summarized separately.

Individual AE listings by subject will be provided.

[REDACTED]

Adverse events (AE) will be classified using the Medical Dictionary for Regulatory Activities (MedDRA) classification system. The severity of the toxicities will be graded according to the NCI CTCAE version 3.0 whenever possible.

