12.5. Deaths

Deaths during the treatment phase and within 30 days from the last dose of study treatment will be tabulated by the primary cause of death and treatment arms. Separate summary tables will be made for the deaths that are suspected to drug related and for those that are considered non-drug related.

The same summary tables will be provided for the deaths that occur during follow-up phase separately.

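### SAP 12.1 allows a follow-up AE table by arm, but late non-SPM events enter only as SAEs the investigator judges related, with the arm known since Amendment 10, so capture can differ by arm

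*SAP*

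**What the plan says.** **Analysis.** SAP 12.1 tabulates AE frequency by body system and preferred term for each regimen "during the Treatment Phase as well as for the Follow-up Phase when appropriate". It gives no criterion for when the follow-up table is appropriate. The same section allows an exact test between arms for AEs or frequencies thought clinically important, without saying whether that extends to follow-up data. Protocol 16.7 is narrower: "AE frequency will be tabulated by body system, MedDRA preferred term for each treatment regimen during the Treatment Phase", with no follow-up table. SAP 12.5 tabulates deaths by primary cause and arm, with separate tables for deaths suspected to be drug related and those not, and adds: "The same summary tables will be provided for the deaths that occur during follow-up phase separately".

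**Collection.** Protocol Appendix 22.1 records all AEs "from the time of signing of informed consent form to 30 days after the treatment discontinuation visit". After that, Protocol 8.1 (After Study Discontinuation) says: "Following 30 days post the treatment discontinuation visit, only SAEs related to maintenance therapy will be collected for the study duration". The immediate-reporting text in Appendix 22.1 repeats the filter, adding to the SAEs of the study and the 30-day window "those made known to the investigator(s) at anytime that are suspected of being related to study drug". SPMs are exempt: "This includes any second primary malignancy, regardless of causal relationship to study medication, occurring at any time for the duration of the study". Table 2 agrees. At the survival follow-up visits the adverse event row is empty and the SPM row is marked.

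**Blinding.** Protocol 10.3: "This is now an open-label protocol", from Amendment 10. SAP 5.1 still describes a double-blind trial.

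**The concern.** Safety of lenalidomide against placebo is the only stated secondary objective, and toxicity that appears after stopping is part of it. A by-arm table invites the reader to compare incidence. For late non-SPM events, however, an event reaches the database only if the investigator suspects study drug. Appendix 22.1 defines suspected to require that the timing relative to study drug makes a causal link possible and that nothing else explains the event well enough. An investigator who knows that the capsules were placebo can hardly reach that judgement. One who knows they were lenalidomide can.

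The same late infection or cytopenia could then be counted in one arm and not in the other. At stake is an apparent late excess on lenalidomide that reflects attribution, possibly with a p-value attached.

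**Working it through.** The plan states no figure for follow-up AEs, so there is nothing to reproduce. The check is first textual, then an illustration on assumed inputs.

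**Step 1: which events pass through an unblinded filter**

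| Event | Filter on relatedness | Judged with arm known |
|---|---|---|
| Any AE up to 30 days after the discontinuation visit | No | Not relevant to capture |
| SPM at any time | No | Not relevant to capture |
| Death at any time | No | Not relevant to capture |
| Later non-SPM SAE, before Amendment 10 | Yes | No |
| Later non-SPM SAE, from Amendment 10 | Yes | Yes |
| Later non-serious AE | Not collected under Protocol 8.1 (the synopsis also mentions related AEs) | As above |

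The exposure is confined to late non-SPM events judged from Amendment 10 on. The synopsis wording is wider than Section 8.1 but is still limited to related events.

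**Step 2: how far attribution alone could move the table**

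Assume equal true late SAE rates in both arms. Let

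- b = share of late SAEs judged under the blind,
- q = attribution probability under the blind, the same in both arms,
- qL and qP = open-label attribution on lenalidomide and on placebo,
- s = share of late SAEs that are SPMs, captured without a filter.

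Ratio of tabulated events, lenalidomide to placebo:

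[s + (1 − s)(b·q + (1 − b)·qL)] / [s + (1 − s)(b·q + (1 − b)·qP)]

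None of these inputs is in the documents. I take q = qL = 0.10 and vary the rest.

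Example with b = 0.5, qP = 0.05, s = 0: numerator 0.5×0.10 + 0.5×0.10 = 0.100; denominator 0.5×0.10 + 0.5×0.05 = 0.075; ratio 1.33. With s = 0.3: 0.3 + 0.7×0.100 = 0.370 over 0.3 + 0.7×0.075 = 0.3525; ratio 1.05.

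| b (judged blind) | s = 0, qP = 5% | s = 0, qP = 0 | s = 0.3, qP = 5% | s = 0.3, qP = 0 |
|---|---|---|---|---|
| 1 | 1.00 | 1.00 | 1.00 | 1.00 |
| 0.75 | 1.14 | 1.33 | 1.02 | 1.05 |
| 0.5 | 1.33 | 2.00 | 1.05 | 1.10 |
| 0.25 | 1.60 | 4.00 | 1.08 | 1.17 |
| 0 | 2.00 | unbounded | 1.10 | 1.23 |

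If qP = qL = 10%, every cell is 1.00: without differential attribution there is no lean. The s = 0.3 columns describe a pooled count. SAP 12.1 tabulates by body system and preferred term, so SPMs do not dilute rows such as infections or blood disorders, and s = 0 is the relevant case there.

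**Step 3: follow-up time**

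Under the synopsis, placebo subjects on treatment at Amendment 10 moved to survival follow-up, while lenalidomide subjects could continue until Amendment 11 stopped them. The arms therefore enter the filtered period at different times, and SAP 12.1 gives no adjustment for follow-up time. More placebo follow-up could push crude counts the other way, so even the sign of the net distortion is not fixed by the documents.

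**The case against.** The strongest reply is that this joins two designs. The SAP is written for the double-blind trial, with co-primary PFS and OS. Under SAP 5.1, subjects who stopped early without progression were followed to progression with AEs assessed, and the relatedness qualifier falls on new SAEs. A follow-up table suits that plan, and attribution then was blind. The current protocol already confines AE tabulation to the Treatment Phase. The SAP table is conditional, and the exact test is optional and not tied to follow-up data. The collection rule is also the same in both arms. Any lean runs against the experimental drug, so it would not falsely reassure about the comparison, and deleting safety output has a cost of its own.

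Most of this stands as a limit on the claim. It does not remove it. The SAP provided still allows the table and gives no criterion for withholding it. Subjects who stop without progression now go to survival follow-up under the filtered rule (Protocol 8.1), so a single table would mix unfiltered early events with filtered later ones. Late non-SPM SAEs that nobody attributes to study drug go unrecorded in both arms, so the table is not a cautious upper bound on late toxicity either.

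On deaths the objection succeeds. A reader might infer that the split by suspected relationship in SAP 12.5 has the same fault. It does not. Survival is followed in all subjects, cause of death is recorded (Protocol 14.2), and no death is lost from the by-arm total. Only the classification after Amendment 10 is open to knowledge of the arm.

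**Conclusion.** The point holds in a limited form. SAP 12.1 and Protocol 16.7 disagree on whether AEs are tabulated by arm in follow-up. If the table is produced, its open-label, non-SPM part can show attribution rather than incidence, to the apparent disadvantage of lenalidomide. Under the assumed 10% attribution (blinded, and open-label on lenalidomide) and equal true rates, the tabulated ratio runs from 1.00 (all judged blind) through 1.33 to 2.00 (half blind, placebo attribution 5% or 0, no SPMs) to higher values as the blinded share falls. With 30% SPMs in a pooled count it stays between 1.00 and 1.23. The documents do not say which case applies.

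Two stronger readings are not supported. A reader might infer that the table leans against lenalidomide by construction; it does not, because the rule is common to both arms and a lean needs differential attribution after unblinding. A reader might also put counts on it: 160 × 0.20 = 32 subjects with late SAEs per arm, times attribution of 10%, 20% or 30%, gives about 3, 6 or 10 against 0. That is an extreme corner. It assumes a 20% incidence, no event judged blind, no placebo attribution and no SPMs.

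**What to change.** 1. In SAP 12.1, remove the by-arm AE tabulation for the Follow-up Phase and state that no exact test will be applied to follow-up AEs. This aligns the SAP with Protocol 16.7.
2. Compare late safety between arms only on events captured regardless of causality: SPMs and all-cause deaths, with deaths by primary cause. Show follow-up time by arm beside them, given the different entry into follow-up at Amendment 10.
3. Present other late related SAEs as a listing, or as a table split at Amendment 10, labelled *investigator-attributed SAEs, not an incidence comparison*.
4. In SAP 12.5, keep the split of follow-up deaths by suspected relationship as descriptive only, with a footnote that attribution after Amendment 10 was unblinded.

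This is SAP wording and needs no new data. The cost is one by-arm safety table lost or relabelled. The late SAEs that were collected remain visible in the listing.

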12.2. Clinical Laboratory Evaluations

Laboratory data will be graded according to NCI CTCAE version 3.0. Shift tables demonstrating the changes from baseline to the worst severity grade observed during the treatment phase will be displayed for each treatment arm for relevant lab parameters for hematology, chemistry, and urinalysis.

12.3. Vital Sign Measurements

For vital signs, cross-tabulations showing the number of subjects with values below, within and above the normal ranges pre-treatment versus post-treatment will be summarized by treatment arm for the treatment phase. For weight, means, medians, standard deviations, minimum, and maximum will be provided by cycle.

12.4. Electrocardiogram (ECG)

ECG results by visit will be summarized by treatment arm. In addition, shift tables for ECG evaluations from baseline to the worst category during the treatment will be provided for each treatment arm.

12.5. Deaths

Deaths during the treatment phase and within 30 days from the last dose of study treatment will be tabulated by the primary cause of death and treatment arms. Separate summary tables will be made for the deaths that are suspected to drug related and for those that are considered non-drug related.

The same summary tables will be provided for the deaths that occur during follow-up phase separately.

13. OTHER TOPICS

13.1. Quality of Life

The Health-Related Quality of Life (HRQL) outcomes assessment include Functional Assessment of Cancer Therapy-Leukemia (FACT-Leu) and EQ-5D.

The subscale scores at each assessment as well as the changes from baseline for post-baseline assessments will be summarized and compared between treatment groups using repeated measures of ANOVA/ANCOVA using the baseline scores as covariates where appropriate. In addition, frequency tables for categorized change from baseline scores (Improvement, No Change, and Worsening) will be presented by treatment group.

Various schemes will be assessed for missing data imputation if needed.

14. INTERIM ANALYSIS

14.1. Administration of the Interim Analyses

An independent DMC will be convened which will be composed of medical oncologists with experience in treating subjects with CLL and a statistician, all of whom are not otherwise involved in the study as investigators. An independent unblinded statistician will perform the interim analyses. The DMC will review safety data on an ongoing basis including adverse events and clinical laboratory data. During the course of the study, the DMC will review the efficacy data in accordance with the guidelines for the pre-planned interim analyses. Operational details for the DMC will be provided in the DMC charter.

The interim analysis results will not be disseminated among investigators and those directly involved with the study conduct unless recommended by the DMC.

14.2. Statistical Approaches for Control of Alpha and Other Considerations

The co-primary efficacy variable, OS, will be compared between the 2 treatment arms using a group sequential log-rank test corresponding to 2 unequally spaced analyses: one interim analysis at approximately 60% information for OS (performed at the same time as the primary analysis for PFS, ie, after about 160 subjects progressed or died) and one final analysis at 100% information after 160 subjects die. The boundary for declaring superiority for the treatment arm is based on an alpha-spending function of the O'Brien-Fleming type with overall $\alpha = 0.025$, two-sided.

At the interim analysis for OS, a log-rank statistic will be calculated and compared with the upper (superiority) boundary. If the value of the log-rank statistic is above this upper boundary, a claim of superiority for the treatment arm could be considered.

Equivalently, the p-value for the two-sided log-rank test will be calculated and a superiority claim for the lenalidomide arm considered if the p-value is less than the nominal p-value corresponding to these boundaries. The table below gives the nominal p-values for rejecting the null hypothesis corresponding to the O'Brien-Fleming boundaries. (The interim bound is approximate and will be re-calculated based on the amount of information available when the interim analysis is actually performed.)

[REDACTED]

[REDACTED]	[REDACTED]	[REDACTED]
[REDACTED]	[REDACTED]	[REDACTED]
[REDACTED]	[REDACTED]	[REDACTED]
[REDACTED]		

In addition to the log-rank test comparing the 2 arms, conditional and predictive power will be calculated at this interim analysis, together with estimation of the hazard ratio and its 95% confidence interval.

[REDACTED]
